5.3.2 Handling of Dropouts or Missing Data

Missing data in efficacy analysis:

For the primary endpoint – IFN gene signature – the last available value either at Visit 9 or 12 will be used for the ANCOVA model.

Missing items in questionnaires:

- SLEDAI-2K and SELENA SLEDAI:
 - At visit 6, 9 and 12 (SLEDAI-2K) or at visit 9 and 12 (SELENA-SLEDAI flare index) respectively, for descriptors “Urinary casts, Hematuria, Proteinuria, Pyuria, Low complement, Increased DNA binding, Thrombocytopenia, Leukopenia”, if value “Not done” is recorded because of no urinary/lab results available, corresponding descriptor from previous visit will be used
 - Other missing data should be considered as not present (protocol rule: items should be recorded if the descriptor is present at the time of the visit or in the preceding 10 days)
- CLASI: missing data will not be replaced. The score will be considered as missing.
- SF-36: scores for each scale are calculated for respondents completing 50% or more of the items within a scale. Among these respondents, the value for any missing item is imputed as the mean value for non-missing items (John E. Ware)
- FACIT fatigue: if there are missing items, subscale scores can be prorated. This is done by multiplying the sum of the subscale by the number of items in the subscale, then dividing by the number of items actually answered. When there are missing data, prorating by subscale in this way is acceptable as long as more than 50% of the items were answered (e.g., a minimum of 4 of 7 items, 4 of 6 items, etc). (Facit Administration and Scoring Guidelines)
- BILAG: For renal BILAG change in renal function over the last four weeks: if previous renal function is not known it will be assumed to be normal and urinalysis will be given values of 0, serum creatinine will be given a value of 100 µmol/L and creatinine clearance (GFR) will be given a value of 100 mL/min. The results entered at the first assessment will be carried forward unless replaced by new values and they should be overwritten if no longer applicable (DA Isenberg). For other cases, score is calculated with the available data.

Statistical Analysis Plan

Study Name: IFN-K-002

SAP version & date: v4, 18/Jun/2018

Missing or incomplete dates:

For calculation / sorting / assignation based on dates (e.g., treatment emergent AEs, concomitant medications...), the following rules will apply:

- The most conservative approach will be considered (i.e., if the onset date of an AE/concomitant medication is missing / incomplete, it will be assumed to have occurred during the study treatment phase (i.e., a TEAE for AEs) except when the partial onset date or other available data indicates differently (e.g., start date day missing, but month before the month of baseline date, or stop date before baseline date)).
- Medical history or disease diagnosis with missing/incomplete date will be assumed to have occurred before any study treatment except when the partial onset date or other available data indicates differently.
- Assignations based on dates will be reviewed and confirmed or infirmed during the data review meeting

No other missing data will be imputed, and all available efficacy and safety data will be included in data listings and tabulations.

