10.9.1 Screening visit (Visit 1; Week -4 to 0)

Patients will undergo a screening visit to be evaluated for eligibility. Rescreening is not allowed.

At the screening visit, after patients have provided signed informed consent to participate in the study, the following activities will be carried out:

- Collect demographic data, including race
- Record SLE-specific and general medical history, including history of alcohol, drug, and tobacco use. In addition, for US patient ONLY, screening test(s) for malignancy within the previous 12 months according to ACS (please refer to appendix 12) has(ve) to be documented in the medical record
- Record prior medication and vaccination
- Assess disease activity scores:
 - SLEDAI-2K
 - PGA
 - BILAG-2004 index
- Perform complete physical examination, including body temperature, weight and height
- Measure vital signs – brachial pulse and blood pressure to be taken after 3 minutes of rest in a supine position

- Perform a gynecological examination, including examination of the cervix, cervical swabbing for cytological examination (PAP smear) and detection of high risk HPV (by RT qPCR); unless performed and documented within 3 months prior to first study product administration
- Perform a 12-lead ECG
- Perform urinalysis, including dipstick and microscopic examination
- Obtain blood sample for:
 - Serum pregnancy test for female patients of childbearing potential
 - Hematology, coagulation (INR, PT, PTT, fibrinogen), biochemistry (complete)
 - Viral serology (screening for HBV [HBsAg], HCV, HIV, CMV, VZV, EBV, HTLV-1, HTLV-2, and HSV-1, HSV-2)
 - Inflammatory markers (C3, C4, CH50)
 - Anti-dsDNA antibodies
 - ANA
 - IFN gene signature (by RT-qPCR)
- Evaluate eligibility

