4.1 Efficacy endpoints

4.1.1 Primary efficacy endpoint(s)

Two co-primary endpoints are evaluated in the trial:

- Change from baseline in the expression of IFN-induced genes at Week 36.
- Response to treatment with IFN-K as measured by the British Isles Lupus Assessment Group (BILAG)-based Composite Lupus Assessment (BICLA) response criteria at Week 36:
 - All BILAG A scores at baseline improve to B/C/D and all BILAG B scores improve to C/D at Week 36
and
○ No BILAG worsening in other body systems: no new BILAG A or ≥ 2 new BILAG B scores at Week 36
and
○ No worsening in SLEDAI-2K total score at Week 36 compared with baseline
and
○ No deterioration in PGA (< 10% worsening) on VAS 100 mm at Week 36 compared with baseline
and
○ No addition or increased dose level of anti-malarial drugs or immunosuppressive drugs or corticosteroids between Week 24 and Week 36 (this criterion will be identified by medical review)

Statistical Analysis Plan

Study Name: IFN-K-002

SAP version & date: v4, 18/Jun/2018

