5.4 Data handling conventions

5.4.1 Baseline definitions

For IFN gene signature, only Week 0 (visit 2) will be considered as baseline.

For BILAG scores, a baseline value will be defined for each body system. This baseline will be the value at Week 0 (visit 2).

For other efficacy and safety endpoints the last observation prior to the first dose of study treatment administration will be used as the baseline value. This will usually correspond to the measurement performed at Week 0 before first-dose. However, in case of missing value at Week 0, the last available value recorded during screening will be used as baseline value.

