7.5 LLDAS

Analysis for LLDAS, initially not planned in the protocol, will be done.

8 Software documentation

All summaries and statistical analyses will be generated using SAS version 9.4 or higher.

Statistical Analysis Plan

Study Name: IFN-K-002

SAP version & date: v4, 18/Jun/2018

9 Derived data

Derived variable	Derivation algorithm
Change from baseline to visit V (continuous)	
Change from baseline of variable X=X(Visit V)-X(Baseline)
 
 ○ Negative values indicate a decrease in X ○ Positive values indicate an increase in X
Percent change from baseline to visit V (continuous)	
Percent change from baseline of variable X=100 *[X(Visit V)-X(Baseline)]/X(Baseline)
 
 ○ Negative values indicate a decrease in X ○ Positive values indicate an increase in X
Treatment Compliance (continuous)	
The compliance Ci for patient i will be computed according to:
 $C_i = \frac{D_i^t * 100}{D_i^p}$ 
where D_i^p mg is the total amount (mg) of IP prescribed to patient i and D_i^t is the total amount (mg) of IP actually taken by the patient during the study i.e., before the end of study for patient i.

Treatment compliance (categorical) (if relevant)	
Categorial variable with three modalities:
 
 • $C_i < 80\%$ • $80\% \leq C_i < 120\%$ • $C_i \geq 120\%$
Event Duration	$(\text{End Date}) - (\text{Start Date}) + 1$
BILAG score	See BILAG-2004 Index scoring
SLEDAI-2K and SELENA SLEDAI	Sum of the weights
SLICC/ACR	Sum of items
CLASI	Sum of items
FACIT	See FACIT-Fatigue Subscale Scoring Guidelines (Version 4)

Statistical Analysis Plan

Study Name: IFN-K-002

SAP version & date: v4, 18/Jun/2018

Derived variable	Derivation algorithm
SF-36	See SF-36 Health Survey, Manual and Interpretation Guide
Time to event SLE flare	
SLE flare will be identified in BILAG-2004 scoring.
 
SLE flares are predefined as a BILAG A or B score due to items that were new or worse in any of the eight organ system (Isenberg et Al).
 
For patient with a SLE flare: Time to event = Visit date of corresponding BILAG – Date of Week 0 + 1
 
For patient without SLE flare: Time to event = Date of Week 36 (or date of end of study for patients prematurely withdrawn before Week 36) – Date of Week 0 +1

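### SAP 5.3.2 leaves Week 0 out of its carry-forward for SLEDAI laboratory items, so read literally an item 'Not done' at baseline scores 0 and can cause false failure on BICLA, SRI-4 and the SLEDAI response

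*SAP*

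**What the plan says.** SAP 5.3.2 has two rules for missing SLEDAI-2K and SELENA-SLEDAI items.

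- **Laboratory rule.** It names urinary casts, hematuria, proteinuria, pyuria, low complement, increased DNA binding, thrombocytopenia and leukopenia. Its scope is "At visit 6, 9 and 12 (SLEDAI-2K) or at visit 9 and 12 (SELENA-SLEDAI flare index) respectively". If one of these is 'Not done' for lack of a result, the "corresponding descriptor from previous visit will be used".
- **Default rule.** "Other missing data should be considered as not present".

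Visit 2 (Week 0) is not in the first rule's list. The total score is defined in SAP section 9 as "Sum of the weights".

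For endpoints other than the gene signature and BILAG, SAP 5.4.1 adds that "in case of missing value at Week 0, the last available value recorded during screening will be used as baseline value". It does not say whether a value means the total score or a single item.

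Two kinds of endpoint depend on the baseline total. BICLA requires "No worsening in SLEDAI-2K total score at Week 36 compared with baseline" (SAP 4.1.1). SRI-4 and the SLEDAI response each require a fall of at least 4 points (SAP 4.1.2.1).

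**The concern.** The SAP accepts after baseline that a laboratory item not measured is not the same as an item absent, but does not extend this to Week 0. There the default rule scores the item at the lowest possible value. The total then exists, so 5.4.1 has no evident reason to look back to screening. Nor does the per-protocol definition (SAP 3.3.2) catch the case, because it excludes only patients whose baseline SLEDAI-2K is missing.

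An understated baseline makes a true improvement look smaller, or look like worsening. That matters because SLEDAI enters the second co-primary endpoint and two secondary responses. SAP 5.2.4.1 interprets observed BICLA differences of 10% and 15% regardless of significance, and SAP 5.2.4.3.1 allows SRI-4 to become the primary endpoint in later development. BICLA power is planned at only 73%.

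**Working it through.** **1. Is there a better source than zero?** Protocol 10.9.1 schedules a SLEDAI-2K at Visit 1. It also schedules urine testing ("Perform urinalysis, including dipstick and microscopic examination"), hematology, C3/C4/CH50 and anti-dsDNA. Visit 2 follows within 28 days (Protocol 10.9.2). For comparison, the existing rule accepts a Week 24 descriptor at Week 36, which is 12 weeks old. SELENA-SLEDAI is first scored at Visit 2, so it has no screening form of its own. Appendix 4 gives its descriptors the same weights as Appendix 2.

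**2. How many points can be zeroed?** Appendix 2 weights for the eight items: 4+4+4+4+2+2+1+1 = 22. Low complement plus DNA binding: 2+2 = 4.

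**3. When does a limb fail falsely?** Let r be the true reduction and u the weight zeroed at Week 0 for items truly present then, with Week 36 scored correctly. The observed reduction is r − u.

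- BICLA limb: truly met if r ≥ 0, observed as met if r − u ≥ 0. False failure when 0 ≤ r < u.
- SRI-4 and SLEDAI-response limbs: truly met if r ≥ 4, observed as met if r − u ≥ 4. False failure when 4 ≤ r < 4+u.

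| u | BICLA limb lost at r | SRI-4 and SLEDAI-response limbs lost at r |
|---|---|---|
| 1 | 0 | 4 |
| 2 | 0-1 | 4-5 |
| 4 | 0-3 | 4-7 |

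Since r − u never exceeds r, no false success arises on these limbs.

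**4. Examples.**

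- BICLA limb: rash 2, mucosal ulcers 2 and proteinuria 4 make 8; at Week 36 rash and proteinuria make 6. The true change is −2, a pass. With proteinuria 'Not done' at Week 0, the score goes from 4 to 6, +2, a fail.
- SRI-4 limb: arthritis 4, low complement 2 and DNA binding 2 make 8; at Week 36 the last two make 4. The true change is −4, a pass. With complement 'Not done' at Week 0, the score goes from 6 to 4, −2, a fail.

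**5. The plan's own power figure.** Inputs (SAP 2.3.2): 20.6% against 40.6%, 80 per group, two-sided 5%; stated power 73%. With a continuity correction,

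power = Φ{(d − 1/n − 1.96·SE0)/SE1}, where SE0 = √(2·p̄(1−p̄)/n) and SE1 = √((p0(1−p0)+p1(1−p1))/n).

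Here p̄ = 0.306, SE0 = 0.0729 and SE1 = 0.0711, so power = Φ{(0.2000 − 0.0125 − 0.1428)/0.0711} = Φ(0.628) = 73.5%. Fisher's exact test gives 74.1%, and the uncorrected test 78.9%. The corrected form therefore reproduces the stated figure.

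**6. Effect of losing responders.** Let m be the share of true BICLA responders lost, assumed equal in both arms. The rates become 0.206(1−m) and 0.406(1−m).

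| m (assumed) | Placebo | IFN-K | Difference (points) | Power |
|---|---|---|---|---|
| 0 | 20.6% | 40.6% | 20.0 | 73.5% |
| 1% | 20.4% | 40.2% | 19.8 | 72.8% |
| 2% | 20.2% | 39.8% | 19.6 | 72.1% |
| 5% | 19.6% | 38.6% | 19.0 | 70.0% |

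In patients: 80 × (0.206 + 0.406) = 49 expected responders, so m = 1-5% is about 0.5 to 2.4 patients in the whole trial.

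**The case against.** **SAP 5.4.1 may already cover this.** If its fallback was meant item by item, a 'Not done' at Week 0 would be filled from screening. The default rule is also justified in the SAP by the form's instruction to record items that are present, which suits an unticked box better than a recorded 'Not done'. This stands as an ambiguity. It is therefore too strong to say that the fallback can never apply. But 5.3.2 is the specific item rule, the text never says that 5.4.1 works on items, and two programmers could derive different baselines.

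**Protocol 13.8 says that missing baseline values are not replaced.** Scoring zero is itself a replacement, and 5.4.1 already departs from 13.8.

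**A false BICLA failure should be uncommon.** The patient must meet every other BICLA limb and have a true SLEDAI fall smaller than the zeroed weight. BICLA responders must improve in all baseline BILAG A and B systems, and resolved arthritis alone is worth 4 points. A patient whose A or B grades are simply stable fails BICLA anyway. This stands and limits the size.

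**Errors can cancel.** If an item is 'Not done' at Week 0 and at each later scoring visit, the zero carries through to Week 36, and both scores are understated if the item persists. This also stands.

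**A reader might go further and want the post-baseline carry-forward replaced by central-laboratory results from Weeks 28 and 32.** The documents do not support that. Neither visit schedules anti-dsDNA, and Week 32 has no complement (Protocol 10.9.10 and 10.9.11). Several descriptors also need attribution that a raw result lacks: Appendix 2 excludes infection for hematuria and pyuria, and drug causes for the blood counts. Carrying the scored descriptor forward keeps the investigator's judgement.

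**Conclusion.** The gap is real on the literal text. Visit 2 is outside the laboratory rule, the default scores the item absent, and the SAP does not reconcile this with 5.4.1. On these SLEDAI limbs, with Week 36 scored correctly, the error runs only towards false failure.

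Its size is unknown and probably small, because the documents give no rate of 'Not done' at Week 0. The power range of 72.8% to 70.0% rests on an assumed loss of 1-5% of true responders, equal in both arms, and on the simple two-proportion test, whereas the planned analysis is an adjusted logistic regression.

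Two stronger inferences should not be drawn.

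- A reader might infer bias in favour of IFN-K or an inflated type I error. The zeroing happens before treatment and should be about equally frequent in both arms, so it costs responders and power. The gene-signature endpoint, which is tested first, is untouched.
- A reader might multiply a guessed 5-10% affected by 30-50% with complement and DNA binding both abnormal, and then by the mean planned response of 30.6%, to get a loss of 0.5-1.5 percentage points. That is a ceiling on inputs with no source in the documents: it takes the full 4 points and counts every affected responder as lost.

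This is worth correcting but does not threaten the trial's validity.

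**What to change.** In SAP 5.3.2, add Visit 2 to the carry-forward rule: a laboratory descriptor 'Not done' at Week 0 takes its value from the Visit 1 SLEDAI-2K form, for both SLEDAI-2K and SELENA-SLEDAI. State that this item rule is applied before 5.4.1, so that 5.4.1 acts only if the total is still missing. Appendix 4 prints weights but no definitions for SELENA-SLEDAI, so the team should confirm that the eight descriptors map one to one. Leave the rule for Visits 6, 9 and 12 as it is.

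A count by arm of Week 0 'Not done' items, reported with the results, would show how much this mattered.

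The cost is about two sentences and a small derivation from data already collected. It must be settled before database lock and unblinding, as SAP section 1 requires.

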5.3.3 Interim Analyses and Data Monitoring

No formal interim data analysis is planned for the study.

An Independent Data Safety Monitoring Board (iDSMB) has reviewed safety data on a regular basis during the course of the study. More details are provided on the iDSMB charter.

5.3.4 Multicentre studies

Randomized patients are included in 65 sites. With regards to the large number of sites compared to the planned number of patients, no adjustment for centre effect will be done. In addition, randomization was centralized and using a minimization.

5.3.5 Multiple Comparison/Multiplicity

This study has 2 co-primary endpoints tested by sequence (ie: First, the first co-primary endpoint will be tested at an error probability of 5% for a 2-sided test). If and only if this Null-hypothesis can be rejected, the second co-primary endpoint will be tested also at an error probability of 5% for a 2-sided test). Consequently, no problem for multiplicity in this study.

Statistical Analysis Plan

Study Name: IFN-K-002

SAP version & date: v4, 18/Jun/2018

5.3.6 Use of an "Efficacy Subset" of Patients

Two efficacy analyses populations were defined, the FAS and the PP. The definition of these populations is given in Section 3.3. The primary efficacy analysis will be conducted on the FAS. The PP population will be used to conduct a sensitivity analysis and assess the robustness of the primary efficacy analysis conclusions. Any substantial difference between the two analyses will be explored and discussed.

Some unblinding (for SAEs/SUSARs reporting and/or upon FDA request) have led to involuntary potential access to unblinded information by the concerned investigator. An analysis excluding these patients will be done for the primary efficacy analysis to assess the robustness of the expected results.

5.3.7 Active-Control Studies Intended to Show Equivalence

Not applicable.

5.3.8 Examination of Subgroups

No subgroups have been defined.

5.4 Data handling conventions

5.4.1 Baseline definitions

For IFN gene signature, only Week 0 (visit 2) will be considered as baseline.

For BILAG scores, a baseline value will be defined for each body system. This baseline will be the value at Week 0 (visit 2).

For other efficacy and safety endpoints the last observation prior to the first dose of study treatment administration will be used as the baseline value. This will usually correspond to the measurement performed at Week 0 before first-dose. However, in case of missing value at Week 0, the last available value recorded during screening will be used as baseline value.

5.4.2 Outliers

All outlier data will be reviewed during the data-review meeting and decisions regarding their use in the statistical analyses will be made.

Statistical Analysis Plan

Study Name: IFN-K-002

SAP version & date: v4, 18/Jun/2018

5.4.3 Windows for time points

All visits will be analyzed as entered in the database except if otherwise specified during the data-review meeting.

5.4.4 Retest and Unscheduled visits

During the data review meeting, any data from unscheduled visit which must be taken into account in the analysis will be identified.

Other data from unscheduled visits will only be tabulated in listings.

6 Interim analysis

No interim analysis is planned.

7 Modifications from the statistical sections in the protocol

7.1 Analysis dataset

Intention to Treat population has been re-labeled Full Analysis Set.

7.2 Efficacy analysis

7.2.1 Primary efficacy analysis

A mixed model for repeated measures with random intercept using all measurements available (IFN gene signature/Score) until Week 36 has been added for the first co-primary endpoint to compute the estimate of the between group difference in change from baseline at week 36 as a sensitivity analysis.

7.2.2 Secondary efficacy & exploratory analyses

The criterion “composite SRI-4 response (tapering CS \leq 5mg and \leq 7.5mg)”, initially not planned in the protocol, will be analyzed (same method as SRI-4).

The analysis on exploratory endpoint “changes in Lupus Therapy” has been removed because it is redundant with the BICLA and LLDAS analyses.

Statistical Analysis Plan

Study Name: IFN-K-002

SAP version & date: v4, 18/Jun/2018

7.3 Adverse events

Analysis of solicited local & systemic reactions 1-hour post study product administration was planned in the protocol. Time of these AEs was not recorded into the eCRF. This analysis will not be done.

7.4 Laboratory

Analysis on percent change was planned in the protocol. This type of analysis is not always relevant. This analysis will be replaced by an analysis on the change.

7.5 LLDAS

Analysis for LLDAS, initially not planned in the protocol, will be done.

8 Software documentation

All summaries and statistical analyses will be generated using SAS version 9.4 or higher.

Statistical Analysis Plan

Study Name: IFN-K-002

SAP version & date: v4, 18/Jun/2018

9 Derived data

Derived variable	Derivation algorithm
Change from baseline to visit V (continuous)	
Change from baseline of variable X=X(Visit V)-X(Baseline)
 
 ○ Negative values indicate a decrease in X ○ Positive values indicate an increase in X
Percent change from baseline to visit V (continuous)	
Percent change from baseline of variable X=100 *[X(Visit V)-X(Baseline)]/X(Baseline)
 
 ○ Negative values indicate a decrease in X ○ Positive values indicate an increase in X
Treatment Compliance (continuous)	
The compliance Ci for patient i will be computed according to:
 $C_i = \frac{D_i^t * 100}{D_i^p}$ 
where D_i^p mg is the total amount (mg) of IP prescribed to patient i and D_i^t is the total amount (mg) of IP actually taken by the patient during the study i.e., before the end of study for patient i.

Treatment compliance (categorical) (if relevant)	
Categorial variable with three modalities:
 
 • $C_i < 80\%$ • $80\% \leq C_i < 120\%$ • $C_i \geq 120\%$
Event Duration	$(\text{End Date}) - (\text{Start Date}) + 1$
BILAG score	See BILAG-2004 Index scoring
SLEDAI-2K and SELENA SLEDAI	Sum of the weights
SLICC/ACR	Sum of items
CLASI	Sum of items
FACIT	See FACIT-Fatigue Subscale Scoring Guidelines (Version 4)

Statistical Analysis Plan

Study Name: IFN-K-002

SAP version & date: v4, 18/Jun/2018

Derived variable	Derivation algorithm
SF-36	See SF-36 Health Survey, Manual and Interpretation Guide
Time to event SLE flare	
SLE flare will be identified in BILAG-2004 scoring.
 
SLE flares are predefined as a BILAG A or B score due to items that were new or worse in any of the eight organ system (Isenberg et Al).
 
For patient with a SLE flare: Time to event = Visit date of corresponding BILAG – Date of Week 0 + 1
 
For patient without SLE flare: Time to event = Date of Week 36 (or date of end of study for patients prematurely withdrawn before Week 36) – Date of Week 0 +1

Ethnic origin	Ethnic will be derived using race variable existing in the CRF. The other ethnic origin “Black, Asian, Caucasian or Hispanic” will be re-classified in the predetermined modalities (Black, Asian, Caucasian/Hispanic)

Statistical Analysis Plan

Study Name: IFN-K-002

SAP version & date: v4, 18/Jun/2018

10 Tables, Figures and Listings

